#### 7. ASSESSMENTS

Every effort should be made to ensure that the protocol-required tests and procedures are completed as described.

All procedures should be followed within the allowed flexibility windows as outlined in the Study Calendar.

### 7.1 Safety Assessments

#### 7.1.1 Pregnancy Testing

All pregnancy tests used in this study, either urine or serum, must be performed by a certified laboratory. For female patients of childbearing potential, 2 negative pregnancy tests are required before receiving investigational product - 1 negative pregnancy test during screening period (within 28 days of first dose of study drugs), and 1 at the baseline visit immediately before administration of investigational product.

Following a negative pregnancy test result at screening, appropriate contraception must be commenced and a further negative pregnancy result will then be required at the baseline visit before the patient receives the investigational products. Pregnancy tests will also be routinely repeated on Day 1 of every cycle (prior to dosing of study drugs) during the active treatment period, at the end of study therapy, and additionally whenever 1 menstrual cycle is missed or when potential pregnancy is otherwise suspected. In the case of a positive hCG test and confirmed pregnancy, the patient will be withdrawn from administration of investigational products and will be withdrawn from the study. Additional pregnancy tests may also be undertaken if requested by the Institutional Review Board (IRB) or if required by local regulations.

## 7.1.2 Contraception Check

Male patients who are able to father children and female patients who are of childbearing potential, who are, in the opinion of the investigator, sexually active and at risk of pregnancy with their partner(s), will need to affirm that they meet the criteria for correct use of 2 highly effective (<97% failure rate) methods of contraception.

Adequate methods of contraception include:

- Total abstinence when this is in line with the preferred and usual lifestyle of the subject.
   Periodic abstinence (e.g., calendar, ovulation, symptothermal, post-ovulation methods) and withdrawal are not acceptable methods of contraception;
- Female sterilization (have had surgical bilateral oophorectomy with or without hysterectomy) or tubal ligation at least six weeks before taking study treatment and thus are not considered to be of child-bearing potential. In case of oophorectomy alone, only when the reproductive status of the woman has been confirmed by follow up hormone level assessment;
- Male sterilization (at least 6 months prior to screening). For female subjects on the study, the vasectomized male partner should be the sole partner for that subject;
- Combination of any of the following two (a+b or a+c or b+c):
  - Use of oral, injected or implanted hormonal methods of contraception or other forms of hormonal contraception that have comparable efficacy (failure rate <1%), for example hormone vaginal ring or transdermal hormone contraception;
  - b. Placement of an intrauterine device (IUD) or intrauterine system (IUS);
  - c. Barrier methods of contraception: Condom or Occlusive cap (diaphragm or cervical/vault caps) with spermicidal foam/gel/film/cream/ vaginal suppository.

In case of use of oral contraception, women should have been stable on the same pill before taking study treatment.

Note: Oral contraceptives are allowed but should be used in conjunction with a barrier method of contraception due to unknown effect of drug-drug interaction. Women are considered post-menopausal and not of child bearing potential if they have had 12 months of natural (spontaneous) amenorrhea with an appropriate clinical profile (e.g. age appropriate, history of vasomotor symptoms) or have had surgical bilateral oophorectomy (with or without hysterectomy) or tubal ligation at least six weeks ago. In the case of oophorectomy alone, only when the reproductive status of the woman has been confirmed by follow up hormone level assessment is she considered not of child bearing potential.

The investigator or his/her designee will discuss with the patient the need to use 2 contraception methods consistently and correctly and document such conversation in the patient's chart. In addition, the investigator or his/her designee will instruct the patient to call immediately if one or both selected contraception methods are discontinued, or if pregnancy is known or suspected in the patient or the patient's partner.

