- 9. Subjects must have measurable disease per RECIST v1.1, or patients may have bone metastatic disease evaluable by Prostate Cancer Working Group 3 (PCWG3) for subjects with metastatic castration-resistant prostate cancer (CRPC), or according to tumor evaluation criteria best suited and accepted for the tumor type to be evaluated.
- 10. Subjects must have an Eastern Cooperative Oncology Group (ECOG) performance status 0-1.
- 11. Subjects must have a life expectancy ≥12 weeks.
- 12. Subjects must have normal organ and marrow function as defined below:

- a. Absolute neutrophil count  $\geq 1.5 \times 10^9 / L$ ;
- b. Platelets ≥100 x 10^9/L:
- c. Hemoglobin  $\geq$  9 g/dL or  $\geq$  5.6 mmol/L
- d. Total bilirubin ≤1.5X the institutional upper limit of normal (ULN);
- e. AST(SGOT)/ALT(SGPT) ≤2.5X institutional ULN or ≤5X institutional ULN in the presence of liver metastases;
- f. Renal function defined by serum creatinine ≤ 2X ULN or estimated creatinine clearance ≥30 mL/min according to the Cockcroft-Gault formula.
- 13. Female patients of childbearing potential must have a negative serum or urine pregnancy test at screening (and again at baseline just prior to first administration of study drugs).

Female patients of non-childbearing potential must meet at least 1 of the following criteria:

- Achieved postmenopausal status, defined as follows: cessation of regular menses for at least 12 consecutive months, with no alternative pathological or physiological cause;
- b. Have undergone a documented hysterectomy and/or bilateral oophorectomy;
- c. Have medically confirmed ovarian failure.

All other female patients are considered to be of childbearing potential.

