- 14. Women of childbearing potential and fertile men must agree to use adequate contraception when sexually active from signing of the informed consent form for the full study until at least 6 months after the last study drug administration. Patients must agree to utilize 2 reliable and acceptable methods of contraception simultaneously. A man is considered fertile after puberty unless permanently sterile by bilateral orchiectomy. Men taking part in this study are advised not to father a child during and up to 6 months after treatment; prior to treatment, advice should be sought for conserving sperm due to the chance of irreversible infertility as a consequence of treatment. Female partners of childbearing potential from male study patients have to use adequate contraception / birth control between signing of the informed consent and 6 months after the last administration of the study drug if the male study patient is not sterilized. The investigator or a designated associate is requested to advise the patient how to achieve highly effective birth control. Highly effective (failure rate of less than 1% per year) contraception methods, when used consistently and correctly, include:
  - Combined (estrogen and progestin containing: oral, intravaginal, transdermal) and progestin-only (oral, injectable, implantable) hormonal contraception associated with inhibition of ovulation.
  - Intra-uterine device or intrauterine hormone-releasing system.
  - Bilateral tubal occlusion or vasectomized partner (provided that partner is the sole sexual partner and has received medical assessment of the surgical success).
  - Sexual abstinence (reliability to be evaluated in relation to the duration of the clinical trial and the preferred and usual lifestyle of the patient).

Male patients with a female partner of reproductive potential must use a condom and ensure that an additional form of contraception is also used during treatment and until 6 months after last study drug administration. Patients must agree to utilize 2 reliable and acceptable methods of contraception simultaneously.

- 15. Evidence of a personally signed and dated informed consent document indicating that the patient has been informed of all pertinent aspects of the study.
- 16. Willing and able to comply with scheduled visits, treatment plan, laboratory tests, and other procedures.

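### Section 7.1.2 classes women with tubal ligation as not of childbearing potential, contrary to inclusions 13 and 14, and misstates the failure-rate limit for highly effective contraception

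*Combined protocol and SAP*

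**What the plan says.** **Inclusion 13 (section 4.1)** gives three routes to non-childbearing status: postmenopausal status, documented hysterectomy and/or bilateral oophorectomy, and medically confirmed ovarian failure. It then closes the list: "All other female patients are considered to be of childbearing potential".

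**Inclusion 14 (section 4.1)** applies to sexually active women of childbearing potential and to fertile men, from consent until at least 6 months after the last dose. It states: "Patients must agree to utilize 2 reliable and acceptable methods of contraception simultaneously". Its list of highly effective methods, defined by an annual failure rate below 1%, includes "Bilateral tubal occlusion or vasectomized partner".

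**Section 7.1.2 (Contraception Check)** requires sexually active women of childbearing potential to affirm "correct use of 2 highly effective (<97% failure rate) methods of contraception". Its bullet on female sterilization covers women with "tubal ligation at least six weeks before taking study treatment and thus are not considered to be of child-bearing potential". A later note begins "Women are considered post-menopausal and not of child bearing potential if they have had 12 months of natural (spontaneous) amenorrhea" and ends its list of qualifying routes with "tubal ligation at least six weeks ago". For hormonal methods the same section refers to "hormonal contraception that have comparable efficacy (failure rate <1"%. Its last paragraph tells the investigator to discuss with the patient the need for two methods and to record that discussion.

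**The concern.** The same woman has two statuses in one protocol. Under section 4.1, a woman with tubal ligation is of childbearing potential and her ligation counts as one of two required methods. Under section 7.1.2, she is not of childbearing potential, so the affirmation does not apply to her. Site staff who work from 7.1.2, the text written for the contraception check, could leave out the second method that inclusion 14 requires of her throughout treatment and for at least 6 months afterwards.

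The failure-rate figure is a separate defect in the same section. As written, it would let almost any method count as highly effective, and it disagrees with both inclusion 14 and the figure 7.1.2 gives for hormonal methods. Both defects lie in operative text that protects participants from pregnancy during exposure to the study drugs.

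**Working it through.** No statistical figure is involved, so the check is a comparison of the texts with simple counts.

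**Step 1: status of a woman with tubal ligation.**
- Inclusion 13: not among the three routes, so the closing sentence makes her of childbearing potential.
- Section 7.1.2, sterilization bullet: not of childbearing potential if the ligation was at least six weeks before treatment.
- Section 7.1.2, later note: the same classification, inside the sentence that defines postmenopausal status.
- Conflicting statements: 1 + 1 = 2. The repetition makes a stray phrase an unlikely explanation.

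**Step 2: number of further methods, if she is sexually active.**
- Inclusion 14: 2 methods required − 1 (tubal occlusion) = 1 further method.
- Section 7.1.2 affirmation: among women it covers only those of childbearing potential, and 7.1.2 has classed her outside that group, so 0 further methods are affirmed.
- Difference: 1 − 0 = 1 method.

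The layout of the 7.1.2 list points the same way. Abstinence, female sterilization or tubal ligation, and male sterilization each have their own bullet. A pair of methods is required only within the last bullet, which covers hormonal methods (a), intrauterine devices or systems (b) and barrier methods (c).

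**Step 3: the failure-rate limit.**
- Section 7.1.2, general wording: under 97%, with no time unit.
- Section 7.1.2, hormonal methods: under 1%.
- Inclusion 14: under 1% per year.
- If 97% effectiveness was meant (an assumption; the documents do not say so), the limit would be 100% − 97% = 3%. Read on the same yearly basis, 3% / 1% = 3 times the limit in inclusion 14. Exchanging failure for effectiveness would therefore not remove the conflict.

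**Step 4: what else depends on the 7.1.2 definition.**
- Pregnancy testing: Study Calendar footnote 3 refers to the definition in the inclusion criterion, so testing of these women is unaffected.
- Eligibility: set by section 4, so unaffected.
- Endpoints, DLT rules and analysis sets: none uses childbearing status.

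**The case against.** The strongest reply is that 7.1.2 only checks a duty that is set elsewhere. Inclusion 14 binds these women regardless. Exclusion 15 rules out women of childbearing potential who are unwilling or unable to use two highly effective methods. The last paragraph of 7.1.2 tells the investigator to discuss two methods with the patient and does not limit this to women of childbearing potential. No sentence says that a woman with tubal ligation may do without a second method. The 97% figure is an evident slip, and the list of acceptable methods limits its practical effect.

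Much of this stands. A reader might infer that 7.1.2 outright releases these women from the second method. The documents do not support that: the gap arises only through reclassification, inclusion 14 remains in force, and the counselling instruction points towards two methods. A reader might also infer that eligibility or pregnancy testing is in doubt, but section 4 governs the first and calendar footnote 3 the second. Nor does the 97% wording mean that poor methods would be accepted in practice, because the named methods set the practical limit.

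The reply does not remove the conflict. Counselling is not the affirmation, and no text says which definition prevails. The two statements in 7.1.2 cannot both be followed along with inclusion 13. That tubal ligation is itself effective is beside the point: if the sponsor wished to accept it alone, inclusions 13 and 14 would have to change.

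**Conclusion.** The conflict is real and minor. Two statements in 7.1.2 contradict inclusion 13 and the use that inclusion 14 makes of tubal occlusion. Followed as written, 7.1.2 takes women with tubal ligation out of its two-method affirmation, one method short of what inclusion 14 asks of those who are sexually active. The failure-rate limit in 7.1.2 is wrong on any reading considered here.

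The effect is confined to the on-study contraception check for this group and to one incorrect figure. The documents do not give the number of women concerned. The conclusion rests on reading inclusion 13 as a closed list, which its last sentence makes explicit. The 3% figure is illustrative only and rests on the stated assumption about what was meant.

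**What to change.** Amend 7.1.2 as follows.

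1. Delete both statements that tubal ligation confers non-childbearing status.
2. Take tubal ligation out of its free-standing bullet and list it as one method that needs a second. Left where it is, it could still be read as sufficient alone.
3. Align the definition of childbearing potential with inclusion 13, but keep the two stricter conditions in 7.1.2: hormone confirmation after oophorectomy alone, and an appropriate clinical profile for amenorrhea. Simply substituting inclusion 13 would drop both.
4. Replace the 97% figure with the inclusion 14 limit, an annual failure rate below 1%, and state that a barrier method (item c) is accepted as the second method. Without that statement, the new limit would clash with the hormonal-plus-barrier and intrauterine-plus-barrier pairs that 7.1.2 already accepts, since inclusion 14's list of methods under 1% contains no barrier method.

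Section 7.1.1 needs no change, because calendar footnote 3 already ties pregnancy testing to the inclusion criterion. Inclusions 13 and 14, exclusion 15 and the visit schedule also stay as they are.

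The cost is a wording amendment. The downside is that sexually active women with tubal ligation must affirm one further method at the check, which inclusion 14 already requires of them.

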#### 7.1.3 Adverse Events

An adverse event (AE) is the appearance or worsening of any undesirable sign, symptom, or medical condition occurring after signed information consent and study entry. Medical conditions/diseases present before starting study drug are only considered adverse events if they worsen after starting study drug. Abnormal laboratory values or test results constitute adverse events only if they induce clinical signs or symptoms, are considered clinically significant, or require therapy.

Assessment of AEs will include the type, incidence, severity (graded by the National Cancer Institute Common Terminology Criteria for Adverse Events (NCI CTCAE) version 5.0) timing, seriousness, and relatedness.

AEs that occur during the study, including baseline signs and symptoms, will be recorded in MOCLIA. The active reporting period begins from the time that the patient provides informed consent, which is obtained prior to the patient's participation in the study, i.e., prior to undergoing any study-related procedure and/or receiving investigational product, through and including 90 calendar days after the last administration of the investigational product.

The investigator (or physician designee) is responsible for verifying and providing source documentation for all adverse events and assigning the attribution for all adverse events for subjects enrolled.

#### 7.1.4 Laboratory Safety Assessments

The required safety laboratory tests are listed in Table 4 below. Required safety laboratory tests including at minimum: hematology (hemoglobin, platelets, and white blood cells), and chemistry (ALT, AST, alkaline phosphatase, total bilirubin, blood urea nitrogen, creatinine, sodium, potassium, and glucose) must be reviewed prior to study drug administration per the study calendar.

**Table 4: Required Safety Laboratory Tests** 

Hematology	Chemistry	Coagulation	Urinalysis (Dipstick is	Pregnancy Test
Hemoglobin Platelets	ALT AST	PT or INR PTT	urine dipstick for urine protein: If	For female patients of
WBC	Alkaline Phosphatase		positive (≥ 2+), collect 24hr urine or collect spot urine and microscopic (Reflex Testing)	childbearing potential, serum or urine with a sensitivity of ≥ 25 mIU/mL
Absolute Neutrophils	Sodium		Urine dipstick for urine blood: If	
Absolute Lymphocytes	Potassium		positive and clinically	
Absolute Monocytes	Magnesium		indicated collect a microscopic (Reflex Testing)	
Absolute Eosinophils	Chloride			
Absolute Basophils	Total Calcium			
	Total Bilirubin Direct Bilirubin Indirect Bilirubin			
Thyroid Function Tests:	Blood urea nitrogen (BUN) or Urea			
TSH, Free T4 Total T3	Creatinine Uric Acid			

	Glucose (non- fasted)		
Other Tests:	Albumin		
ACTH	Phosphorus or Phosphate		
HBV surface antigen	Total Protein		
Anti-HCV antibody	Amylase		
If Anti-HCV antibody test positive, then HCV RNA	Gamma Glutamyl Transferase (GGT)		
Testosterone (at screening only for CRPC patients)	Creatine Kinase		
	C-reactive Protein (CRP)		
	LDH		
	Lipase		

#### 7.1.5 Physical Examinations and Vital Signs

Patients will have a physical examination (PE) per the study calendar, and will include the measurement of body weight, vital signs and assessment of ECOG performance status. Findings of all physical examinations should be recorded in the source documents, and any change from baseline considered by the investigator to be clinically significant should be recorded as an adverse event in the CRF. At screening only, height will be obtained from the electronic medical record.

Abbreviated PEs should be performed as appropriate at each visit where complete physical exams are not required, with special attention to skin and mucosa, and on an as needed basis for assessment of adverse events. Abbreviated exams should be targeted to specific symptoms or complaints and be consistent with local standard of care.

For treatment involving M6620, a patient's body weight will be measured per study calendar at Day 1 of each dosing cycle, and it will be used to calculate the patient's dose of M6620 for that cycle.

Vital signs will include measurements of blood pressure, pulse rate and temperature (oral, tympanic, temporal or axillary). On Day 1 of each cycle, vital signs should be measured prior to infusion start (pre-dose) of first study drug (if more than one study drug is given) and 1 hour after the start of the infusion of last study drug (if more than one study drug is given). The blood pressure cuff, which has been properly sized and calibrated, should be used to measure blood pressure. The use of automated devices for measuring BP and pulse rate is acceptable.

#### 7.1.6 (12-Lead) Electrocardiograms

A standard 12-lead (with a 10 second rhythm strip) tracing will be used for all electrocardiogram (ECG) assessments.

All patients require a single ECG measurement at baseline and C2D1. Thereafter, on treatment ECGs will be performed as clinically indicated.

Clinically significant findings seen on subsequent ECGs should be recorded as adverse events. In case of QTc > 500 msec, a subsequent ECG should be repeated to verify the result. If ECG is confirmed > 500 msec, local guidelines (e.g. Repeat ECGs, review by cardiologist) should be followed.

#### 7.2 Pharmacokinetic Assessments

All efforts will be made to obtain the PK samples at the scheduled nominal time relative to dosing. However, the exact time of the sample collection will always be noted on the CRF. For samples where nominal time coincides with end of infusion, a sample collected within 10 minutes post end of infusion will not be captured as a protocol deviation, as long as the exact time of the sample collection is noted on the source document and data collection tool (e.g., CRF). If a scheduled blood sample collection cannot be completed for any reason, the missed sample time may be rescheduled with agreement of clinical investigators, patient and sponsor. PK sampling schedule may be modified based on emerging PK data. Details on processes for collection, processing, handling, storage and shipment of these samples will be provided in the Laboratory Manual.

PK samples would be stored in Institutional Tissue Bank (ITB) for ~1.5-2 years, while the clinical data mature and await sample analyses.

#### 7.2.1 Blood for PK Analysis of Avelumab

Blood samples (3.5 ml whole blood at each time point) will be collected for serum PK analysis of avelumab as outlined in the Study Calendar. Pre-dose avelumab PK samples will be collected within 1 hour prior to avelumab infusion. The post-dose avelumab samples should be taken within 10 minutes after the avelumab infusion ends. PK sampling for avelumab will occur as follows: (i) Pre dose and EOI: Cycle 1 Day 1 and cycle 1 Day 15, (ii) Pre dose only: Cycle 3, 6 and (iii) End of treatment sample.

Storage & Processing for PK evaluation:

- 1. Do not draw blood for serum as the first tube. When using a winged blood collection, a 2mL Red tube (optional discard tube) should be used prior to the first specimen collection. The discard tube is used to fill the blood collection set tubing's "dead space" with blood. The discard tube does not need to be filled completely and should be a non-additive or coagulation tube, thus SST cannot be used as discard tube. This step ensures maintenance of the proper blood-additive-ratio of the specimen.
- 2. Collect 3.5 mL of blood in a SST tube with Silica Clot Activator and Polymer Gel.
- 3. Gently invert the tube 5 times to mix the clot activator with blood.
- 4. Allow blood to clot for 30 minutes at room temperature in a vertical position.
- 5. After allowing clot to form, centrifuge the tube for 15 minutes at 1100-1300 x g at +25 degrees Celsius (if refrigerated centrifuge is available, set the temperature at 25 degrees Celsius in

MDACC # 2018-1059 Local Version: 08 November 18, 2022

- order to prevent heating during centrifugation and to optimize flow of the barrier material; flow may be impeded if chilled before or during centrifugation).
- 6. Carefully collect and aliquot the serum equally in 2 separate micronics tubes.
- 7. Put the tubes immediately in the freezer in an upright position at -80 degrees Celsius. If not available, store at -20 degrees Celsius (for a maximum of one month). In case of temperature deviations, the affected samples, the length of deviation and maximum temperature reached should be tracked and promptly communicated to the CRA/CTL.

*If shipment is required:* Ship the samples to the Central Lab in batches in dry ice. Material stored at –20 degrees Celsius must be shipped within a maximum of 1 month from blood draw to central laboratory

- 8. Do not draw blood for serum as the first tube. When using a winged blood collection, a **2mL Red tube (optional discard tube)** should be used prior to the first specimen collection. The discard tube is used to fill the blood collection set tubing's "dead space" with blood. The discard tube does not need to be filled completely and should be a non-additive or coagulation tube, thus SST cannot be used as discard tube. This step ensures maintenance of the proper blood-additive-ratio of the specimen.
- 9. Collect **5 mL** of blood in a SST tube with Silica Clot Activator and Polymer Gel.
- 10. Gently invert the tube 5 times to mix the clot activator with blood.
- 11. Allow blood to clot for 30 minutes at room temperature in a vertical position.
- 12. After allowing clot to form, centrifuge the tube for 15 minutes at 1100-1300 x g at +25 degrees Celsius (if refrigerated centrifuge is available, set the temperature at 25 degrees Celsius in order to prevent heating during centrifugation and to optimize flow of the barrier material; flow may be impeded if chilled before or during centrifugation).
- 13. Carefully collect and aliquot the serum equally in **3** separate micronics tubes.
- 14. Put the tubes immediately in the freezer in an upright position at -80 degrees Celsius. If not available, store at -20 degrees Celsius (for a maximum of one month). In case of temperature deviations, the affected samples, the length of deviation and maximum temperature reached should be tracked and promptly communicated to the CRA/CTL.

Ship the samples in batches in dry ice. Material stored at -20 degrees Celsius must be shipped within a maximum of 1 month from blood draw to central laboratory

